Try to anticipate all reasonably foreseeable sharing so that the consent document can also reflect that information. However, it is acceptable to amend this page later and explain either how re-consent of previously and currently enrolled participants will occur or why re-consent should not be required.

The IRB reviews this page against the consent document (if one exists) to demonstrate the ethical principle of Respect for Persons by confirming that plans for sharing do not go against what participants would understand about the use of their data/specimens.

The IRB also ensures there are adequate protections for the privacy of participants and the confidentiality of participants' data/specimens when data is shared with others.

1. * Is it likely investigators could discover information about child/elder abuse or neglect that would require mandatory reporting by the investigators or staff?

The Code of Virginia requires that most medical personnel and all employees of institutions of higher education report suspected child/elder abuse or neglect.

Yes

No

2. * Is it likely investigators could discover a previously unknown reportable disease or condition that would require mandatory reporting by the investigators or staff (i.e., HIV , coronavirus, hepatitis, etc.)?

Yes No

3. * Will the sponsor or investigator obtain a Certificate of Confidentiality for this study?

Certificates of Confidentiality (CoC) are issued by the National Institutes of Health (NIH), the FDA and CDC to protect identifiable research information from forced disclosure. All human subject research studies regardless of funding can qualify to receive a CoC. A CoC is automatically issued for research that was ongoing on December 13, 2016. or initiated after that date. For more information, see

<https://humansubjects.nih.gov/coc/>

No – Will not obtain CoC for this study

Yes – CoC has been obtained or issued automatically

Yes – CoC request is pending

4. * **Select the way(s) that information or biospecimens (including DNA) may be used by the VCU PI or VCU study team for other future research projects (i.e. analyses beyond/apart from the aims of this study)? See help text for definitions.**

Will use directly identifiable information or specimens.

('Directly identifiable' means that identifiers like name, medical record number, social security number, etc. are included in/attached to the dataset/specimens. Maintaining identifiable data for future research is treated as a registry by the VCU IRB. The IRB must approve the new research use in an amendment to this study or as part of a new study before the project is initiated. VCU IRB studies will be asked more questions about this on a later page)

Will use de-identified or indirectly identifiable information or specimens.

('De-identified' means that a linkage/key code exists that links identifiers to data/specimens. When the researcher holds both the data and the key, the VCU IRB considers the subjects to be readily identifiable. Maintaining identifiable data for future research uses is treated by the IRB as a registry. The IRB must approve

the new research use in an amendment to this study or as part of a new study before the project is initiated. VCU IRB studies will be asked more questions about this on a later page)

Will use anonymized information or specimens.

- (*'Anonymized' means that 1) no linkage/key codes exist that link identifiers to data/specimens; and 2) subjects cannot be readily identified, i.e. no direct or indirect identifiers or identifiable combinations of variables. The VCU IRB considers uses of anonymized data/specimens to not be human subject research.*)

Will use aggregate results (summary-level results), not individual-level information or specimens.

- (*The VCU IRB considers uses of aggregate data to not be human subject research because there are no individual subjects.*)

Will contribute to an existing registry or repository

- (*VCU IRB studies will be asked more questions about this on a later page.*)

- Will not use information/specimens for purposes beyond this study.

- Not sure and will submit an amendment when known

- Other use(s) of individual-level information in a way not listed above

5. * Select the way(s) the VCU PI/study team may share information or biospecimens (including DNA) with other researchers who are not on this study team (i.e. for analyses beyond/apart from the aims of this study). See help text for definitions.

Will share directly identifiable information or specimens with other researchers.

- (*'Directly identifiable' means that identifiers like name, medical record number, social security number, etc. are included in/attached to the dataset/specimens. Maintaining identifiable data for future research uses is treated by the VCU IRB as a registry. The data recipient's use of identifiable data would require them to obtain IRB review. VCU IRB studies will be asked more questions about this on a later page.*)

Will share de-identified or indirectly identifiable information or specimens with other researchers.

- (*'De-identified' means that a linkage/key code exists that links identifiers to data/specimens. The VCU researcher maintains the key but does not share it with any other researchers. The recipient's use of de-identified data/specimens may not be human subject research if there is documentation that the key will never be shared with the recipient, but they should check with their own IRB about review requirements. VCU IRB studies will be asked more questions about this on a later page.*)

Will share anonymized information or specimens with other researchers.

- (*'Anonymized' means that 1) no linkage/key codes exist that link identifiers to data/specimens; and 2) subjects cannot be readily identified (i.e. no direct or indirect identifiers or identifiable combinations of variables). The VCU IRB considers uses of anonymized data/specimens by other researchers to not be human subject research, but the recipient should check with their own IRB about review requirements.*)

Will only share aggregate results (summary-level results), not individual-level information or specimens.

- (*The VCU IRB considers uses of aggregate data to not be human subject research because there are no individual subjects. The data recipient should check with their own IRB about review requirements.*)

- Will contribute to an existing registry or repository (VCU IRB studies will be asked more questions about this on a later page.)

- Will submit data to an NIH genomic data repository (VCU IRB studies will be asked more questions about this on a later page.)

- Will not share information/specimens with other researchers.

- Not sure and will submit an amendment when known
- Other sharing of individual-level information with other researchers

6. * Since you responded in a question above that you may use or share anonymous, individual level data, indicate why the proposed use or sharing of anonymous data/specimens is not inconsistent with what participants would have reasonably understood from the consent document about the uses of their information. (Select all that apply.)

- The consent form states that after identifiers are removed, information or specimens could be used for future research studies without additional informed consent from the subject (this is a new element of consent included in consent templates as of May 2018)
- The consent form or exempt information sheet is silent about whether/how information or specimens could be used for future research studies.
- The information or specimens were/will be obtained under a waiver of informed consent, waiver of HIPAA authorization, or an exempt study that did not use an information sheet.
- Other reason why anonymous use/sharing is not inconsistent with the consent document

7. * The Principal Investigator certifies that prior to releasing an anonymized dataset or anonymized specimens the following conditions will all be met:

- all 18 HIPAA identifiers (including all dates) will be removed;
- all indirectly identifiable data elements (unusual, rare, uncommon data) will be removed, grouped, suppressed, or otherwise transformed to no longer be readily identifiable;
- a different subject ID will be assigned than the one used for the main study and a linkage key will not be kept; and
- the PI will review the dataset/specimens to confirm that the remaining information could not be used alone or in combination with any other information to re-identify the participants represented in the data.

See help text for more information.

- Yes
- No

8. * The Principal Investigator certifies that after the study has been closed with the VCU IRB, the following conditions will be met whenever individual level research information and/or specimens are used or shared:

- The identities of participants who are represented in the dataset/specimens will not be readily ascertainable or otherwise re-identifiable by the recipient;
- If a linkage/code key is created, it will be maintained at VCU and not shared with the recipient under any circumstances;
- The PI will have no knowledge that the remaining information could be used alone or in combination with any other information to identify the individuals represented in the data; and
- The PI agrees to abide by this sharing plan even after the study has been closed with the VCU IRB.

- Yes
- No
- N/A - No sharing will occur

Pertinent Results and Incidental Findings

1. * Is it likely investigators could discover a participant's previously unknown condition (e.g. pregnancy, disease, suicidal thoughts, wrong paternity, genetic results, or other findings that may be of importance to health or well-being) or if a participant is engaging in illegal or reportable activities:

Yes

No

2. * Describe what possible pertinent results or incidental findings stemming from research-only procedures may be discovered.

Pregnancy (collected only for screening).

Arrhythmia on HRV measurement

3. * Explain what actions or procedures research personnel should take to inform the PI of such a discovery :

Pregnancy findings will not constitute contacting the PI and the participant will not be able to participate further in the study since we are not aware of the long-term effects of using a TENS unit while pregnant.

Upon review of the HRV measurements, the PI will contact participants/parents and engage in proper referral procedures if there is evidence of arrhythmia.

4. * Will findings be disclosed to participants and/or any other person/group outside of the study team?

Yes

No

5. * Describe a communication plan addressing:

1. What criteria will be used to determine which pertinent and/or incidental findings will be communicated, including the following for health related findings:

- The reliability of the tests/images, such as being done in a CLIA-certified lab,
- Whether the meaning and significance of the findings are known,
- Whether the findings reveal a significant risk of a serious health condition,
- Whether there is an accepted treatment for the health condition revealed by the findings, and
- The risks both of knowing and not knowing the findings, including risks to family members from genetic testing results.

2. What information will be provided during the consent process about the plans for communicating pertinent and/or incidental findings;

3. Whether the participants will be given the option of refusing communication of some or all types of pertinent and/or incidental findings to themselves, their family members, and/or any other individuals or groups; and

4. To whom and by whom the findings will be communicated, when, and how.

Pregnancy findings:

1. -Pregnancy tests are generally reliable. We will be using a urine test purchased through a trusted clinical manufacturer.

-the meaning and significance of a positive pregnancy test is known, the participant will no longer be eligible to participate in the study.

-the findings of a positive pregnancy test does not reveal a significant risk of a serious health condition

-there are resources and treatment for taking a pregnancy to term or not.

-the risk of a positive pregnancy test could cause potential mental and emotional issues, as well as health concerns to the participants if they have other conditions. the risk of not knowing is that participation in the study and using the TENS unit may cause harm to an embryo/fetus. We do not have solid information on the risks of TENS units on pregnant people.

2. If a participant has a positive pregnancy test, we will only be telling the participant whether they are a child or an adult, which we note in the ICFs.

3. Participants will not have the option to refuse communications for safety reasons. If we identify a situation that requires mandatory reporting (ie child abuse in the context of the pregnancy), we will follow the normal procedures for mandatory reporting.

4. Positive pregnancy tests will be verbally communicated to the adult or child participant by a member of the study team, preferably the PI. The study doctor will be notified so they are aware of the participant's ineligibility to continue with the study. If the parent asks why their child is ineligible, we will tell them that we have many different criteria and

can only tell them/the participant if they are eligible or not, and not the reason why.

Arrhythmia findings:

1. - HRV measurement is generally reliable. HRV measurement will be conducted by study team members with sufficient training to operate the devices. HRV measurements done by a coordinator will be reviewed by the PI for evidence of arrhythmia during the data analysis portion of the study.

- The full meaning and significance of an arrhythmia cannot be concluded with a single test. Proper referral will be given, and it will be the responsibility of the participant and/or their parents to seek specialized testing/care to further analyze.

- Arrhythmia findings may reveal a significant risk of a serious health condition, but further testing and analysis is needed for conclusive results.

- There are a variety of accepted treatments for arrhythmia such as medications, therapies such as vagal maneuvers, cardioversion, catheter procedures or heart surgery.

- The risk of knowing the findings is that participants and/or parents could become distressed upon learning the finding.

- The risk of not knowing the finding is that we would not be able to properly measure HRV which is essential to answering our research questions.

2. Participants will be told during the consent discussion that the investigator will contact them/their parents upon the instance of abnormal findings.

3. Participants will not have the option to refuse communications for safety reasons.

4. Abnormal HRV measurements will be communicated by the PI verbally or by phone/email to the participant and/or their parents upon review of the measurements. The participant will be withdrawn from the study by the study staff if this finding is revealed during their participation, but analysis of these measurements will not happen immediately upon collection, so this is an unlikely occurrence.

Risk Benefit Complete

Protocol Progress:

- INITIAL SETUP
- BACKGROUND, RATIONALE & GOALS
- RESEARCH PLAN
- CONSENT PLAN
- RISKS, PRIVACY & CONFIDENTIALITY
- ⑥ POPULATIONS WITH SPECIAL CONSIDERATIONS
- ⑦ INSTITUTIONAL REQUIREMENTS
- ⑧ DOCUMENTS

Click Continue below to go to the next section

Populations with Special Considerations

1. * Check all participant groups that will be either

a) Specifically included in this study or

b) Discernable in the research data/specimens.

(Selections will branch)

Children

Emancipated minors

Wards of the State

Pregnant women or fetuses

Neonates or Post-delivery Materials

Prisoners

Decisionally Impaired Adults

VCU / VCUHS students or trainees

VCU / VCU Health System employees

Individuals with limited English proficiency

Active military personnel

Student populations in K-12 educational settings or other learning environments

Members of a federally recognized American Indian and Alaska Native tribe

None of the Above

Children

1. * Check all that apply to the study:

- 45 CFR 46.404 **Research involving no greater than minimal risk to children, with adequate provisions for soliciting the assent of the children and permission of their parents or guardians, as set forth in Sec. 46.408**
- 45 CFR 46.405 Research involving greater than minimal risk but presenting the prospect of direct benefit to individual participants
- 45 CFR 46.406 Research involving greater than minimal risk and no prospect of direct benefit to individual participants, but likely to yield generalizable knowledge about the participant's disorder or condition
- 45 CFR 46.407 Research not otherwise approvable which presents an opportunity to understand, prevent or alleviate a serious problem affecting the health or welfare of children. (Research in this category must be reviewed and approved by the Secretary of the Department of Health & Human Services)

2. If multiple categories are selected above, explain which study groups are covered by each selected category (e.g. treatment vs. control groups):

N/A

3. * Describe how you plan to obtain permission of parents or legal guardians. If you have indicated this study will fall into categories 406 or 407, please describe here how you will obtain permission from both parents.

Parents will provide informed consent for their child's participation by signing the consent form. Any questions will be answered. A copy of the informed consent will be given to the parents for their records.

4. * Describe how children will be assented to participate in the study (i.e. what will the study team do during the assent process to ensure the child understands what the research involves).

Children will provide informed assent by signing the form. The form will use lay language so the participant knows what the study procedures entail. Any questions will be answered. The study will be explained in a developmentally and age appropriate manner by using "smaller" words to describe the procedures after it is read verbatim. For example, the section in the consent that describes the TENS units sending electrical signals and communications to the brain will be read that way, but will then be elaborated in more age-appropriate language. Study staff would say something like "and by that, we mean the TENS units help your brain talk to the other parts of your body more clearly, and they work by sending a little bit of electricity through your skin. It is not something that will hurt you- you might just feel like someone is tapping your skin a little bit or you may feel a little twitch". Study staff will ask the child if they feel worried or scared about anything we talked about, and will encourage them to ask questions and let them know they are safe to tell us anything they are thinking during the discussion.

Populations with Special Considerations Section Complete

Protocol Progress:

- INITIAL SETUP
- BACKGROUND, RATIONALE & GOALS
- RESEARCH PLAN
- CONSENT PLAN
- RISKS, PRIVACY & CONFIDENTIALITY
- POPULATIONS WITH SPECIAL CONSIDERATIONS
- ⑦ INSTITUTIONAL REQUIREMENTS
- ⑧ DOCUMENTS

Click Continue below to go to the next section

Study Funding

1. * Have you applied for funding:

Yes

No

2. Is this study already funded:

Yes

No

3. * Select all funding sources for this study (pending or awarded):

Industry

Direct Federal

Indirect Federal

State/Local Government

Non-Profit - Sponsored Project

Non-Profit - Gift

Internal Grant

Investigator/Departmental Funds

None

Other

4. * In addition to providing funding support, what is the funding source's role in this study? Select all that apply:

Solely providing funding support

Providing resources (e.g. study drug, device)

Providing guidance to the researcher but does NOT make decisions about study design

Study design/Creation of the study protocol

Collaborator in the research (helps design and/or conduct the study) [list the funder as a site on the Types of Sites page]

Data or sample analysis regardless of identifiability

5. Select all related funding proposals and contracts that have been submitted through the Division of Sponsored Programs (DSP):

RAMS-SPOT ID# (FP/PT/PD#)

Direct Sponsor

PI Title

Status

Start

End

There are no items to display

Types of Sites

VCU Site Information

1. * Select all VCU sites that will be utilized in this study:

- Children's Hospital of Richmond at VCU**
- Clinical Research Services Unit (CRSU)
- Massey Cancer Center
- VCU Health Community Memorial Hospital
- VCU Health Tappahannock Hospital
- VCU Medical Center**
- Other VCU Health Location**
- VCU Monroe Park Campus
- VCU Qatar
- Other VCU Site**

Non-VCU Site Information

Non-VCU sites should be selected whenever any of the following situations apply:

a) Non-VCU sites that will be collaborating on a VCU-led study (i.e. involved in conducting the research, including being involved in the study interpretation or analysis of data and/or authorship of presentations or manuscripts related to the research.)

b) Non-VCU sites that will be deferring to the VCU IRB for IRB review

c) Non-VCU sites where VCU investigators will be overseeing study interventions or interactions

d) Non-VCU sites/locations where VCU investigators will conduct study activities

2. * Select any of the following non-VCU sites utilized in this study:

- McGuire VAMC
- Foreign Sites
- Other Non-VCU Sites
- No Non-VCU Sites**

3. * Is this a multi-center study being led by VCU?

Yes No

4. For Non-VCU Sites: For each site or institution listed as "Site Engaged -- Requests to Rely on VCU IRB Review," upload:

- Completed Local Context Form for Relying on VCU's IRB

- Site specific informed consent form(s) and HIPAA authorization(s), if applicable

For Foreign Sites: For each Cultural Consultant upload a CV/Biosketch that includes a clear description of cultural expertise:

	Document Name	Document	Version	Date Modified	Uploaded By	Type	Approved
View	FGID Assent/Parental V10.pdf	TENS FGID Assent	0.23	4/23/2024 11:25 AM	[name]	Consent/Assent/Information Sheet	Yes
View	Healthy Control Assent/Parental V10.pdf	TENS HC Assent	0.23	4/23/2024 11:25 AM	[name]	Consent/Assent/Information Sheet	Yes

	Document Name	Document	Version	Date Modified	Uploaded By	Type	Approved
View	Healthy Control Consent	TENS HC Consent V10.pdf	0.22	4/23/2024 11:24 AM	[name]	Consent/Assent/Information Sheet	Yes
View	FGID Consent	TENS FGID Consent V10.pdf	0.22	4/23/2024 11:24 AM	[name]	Consent/Assent/Information Sheet	Yes
View	Best Practice Alert MyChart Message Script	Best Practice Alert MyChart Message Script V2.docx	0.03	3/13/2024 3:52 PM	[name]	Recruitment/Advertising	Yes
View	Flyer	TENS Flyer (Undesigned Language Only) V4.docx	0.07	3/13/2024 3:51 PM	[name]	Recruitment/Advertising	Yes
View	REDCap Study Interest & Screening Form	Study Interest & Screening Form V3.pdf	0.04	3/13/2024 3:51 PM	[name]	Recruitment/Advertising	Yes
View	Daily Recording Diary	Daily Recording Diary V6.pdf	0.06	3/13/2024 3:51 PM	[name]	Research Measure	Yes
View	In-Person Recruitment Script	TENS In Person Recruitment Script V5.docx	0.12	3/13/2024 3:46 PM	[name]	Recruitment/Advertising	Yes
View	Phone Recruitment Script	TENS Phone Recruitment Script V7.docx	0.15	3/13/2024 3:46 PM	[name]	Recruitment/Advertising	Yes
View	Eligible Interest Form Submission Follow-Up Email Recruitment Script	TENS Eligible Interest Form Submission Follow-Up Email Recruitment Script V3.docx	0.06	3/13/2024 3:44 PM	[name]	Recruitment/Advertising	Yes
View	Participant TENS Instructions	TENS Unit Instructions V6.docx	0.11	1/9/2024 1:31 PM	[name]	Other	Yes
View	Screen Fail Contact Information	Screen Fail Contact Information.pdf	0.01	12/6/2023 3:22 PM	[name]	Recruitment/Advertising	Yes
View	Heart Rate Variability Measurements	HRV Measurements for both study visits (V2).pdf	0.02	8/23/2023 11:31 AM	[name]	Research Measure	Yes
View	TENS Unit Manual	TENS Unit Manual (Microcurrent Model).pdf	0.02	8/17/2023 9:07 AM	[name]	Drug/Device Brochure	Yes
View	TENS Unit Photo	TENS Unit Photo (Microcurrent Model).png	0.02	8/17/2023 9:07 AM	[name]	Other	Yes
View	Symptom Questionnaire	GI Symptom Questionnaire (V1).pdf	0.01	4/13/2023 3:11 PM	[name]	Research Measure	Yes
View	Ear Clip Info	TENS Unit Ear Clip Information.docx	0.01	1/20/2023 2:09 PM	[name]	Drug/Device Brochure	Yes
View	IDE Documents	TENS Documentation of NSR determination.docx	0.02	11/29/2022 9:41 AM	[name]	Other	Yes
View	TENS Unit Ear Clip	TENS Ear Clip.jpg	0.01	11/18/2022 12:35 PM	[name]	Other	Yes

	Document Name	Document	Version	Date Modified	Uploaded By	Type	Approved
View	PROC Approval	TENS PROC Approval.pdf	0.01	10/21/2022 12:45 PM	[name]	Ancillary Committee Approval	Not Applicable
View	[name] Trainings (All Merged)	[name] CITI, Bioraft, MERT Trainings (Merged).pdf	0.01	10/20/2022 11:55 AM	[name]	Other	Not Applicable
View	[name] CITI Trainings (All Merged)	[name] CITI Trainings (Merged).pdf	0.01	10/20/2022 11:51 AM	[name]	Other	Not Applicable
View	[name] CITI Trainings (All Merged)	[name] CITI Trainings (Merged).pdf	0.01	10/20/2022 11:49 AM	[name]	Other	Not Applicable
View	[name] CV	[name] CV Signed.pdf	0.01	10/20/2022 11:43 AM	[name]	CV/Biosketch	Yes
View	Basic Participant Information	BasicInformation.pdf	0.01	10/18/2022 3:38 PM	[name]	Research Measure	Yes
View	Screening Form	ScreeningForm.pdf	0.01	10/18/2022 3:37 PM	[name]	Research Measure	Yes
View	[name] CV	[name] CV.docx	0.01	9/12/2022 4:52 PM	[name]	CV/Biosketch	Yes

Personnel

1. * List all VCU/VCUHS personnel who are key study personnel.

Key personnel are defined as including:

- Conflict of interest investigators, including
- the PI
- the Lead Student/Trainee Investigator,
- medically/Psychologically responsible investigator(s)
- FDA Form 1572 investigators, and
- Other personnel whose roles are essential to the conduct of the research.

Note: Individuals who are not key personnel are not required to be listed here, but PIs still bear the responsibility to document the delegation of responsibilities in the study records.

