Week 0 Visit (Baseline): After the signing of the ICF, participants will take a pregnancy test. All other screening questions will have been answered previously in the REDCap Study Interest and Screening Form. If the pregnancy test is negative, the participant will be marked as eligible and assigned a Study ID. Participants will complete the GI Symptom Questionnaire on REDCap via a computer or tablet handed to the participant. Heart rate variability (HRV) will then be collected using a digital HRV device. These devices are commonly used to measure HRV, and this study will not be altering the use of that device for research purposes. To measure HRV, electrode leads connected to the device will be placed on the participant's chest and stomach while they are laying down. HRV will be measured for 15 minutes of supine time and 5 minutes of standing time. Participants will then be hooked up to the TENS microcurrent unit (the unit has a pulse rate from 0.1 - 150 Hz, a pulse width of 2 - 200 mS, and an adjustable pulse amplitude of 0-0.7 mA peak at 1000 ohms- the unit will be set at a pulse rate of 50 and a pulse width of 5ms. The mA will be turned up just until the participant can feel it, and then back down to where they can just not feel it, so specific mA strengths may vary between each participant and session), and heart rate variability will be measured again (supine) for another 30 minutes. The unit will be disconnected and HRV will then again be measured for 15 minutes of supine time and 5 minutes of standing time. The HRV device will continuously measure and the electrodes will not be taken off/the machine will not be turned off in between physical positions and conditions since it gives us information on HRV during episodes of position change. Measurement times, including the start time, time when the participant changes physical position, and end time will be recorded in REDcap. Upon completion of the study visit, HRV data from the device will be exported into software-compatible files on a VCU managed computer. They will then be stored on a VCU managed drive with their Study ID and name of the visit (baseline/follow up) as the title of the file for later use in Kubios, an HRV analysis software. The files generated by the HRV measurement devices include information such as the measurement start and end times and the participants' interbeat intervals (IBI/RR)/ECG during the measurement. Files with this information will only be stored in Kubios and/or the VCU drive until analysis is complete. Following the completion of the HRV measurement, the participant will receive a printout of instructions and a physical demonstration on how to use the unit by an approved study team member and instructed to use it at a consistent time each day for 2 hours daily over 4 weeks. The participant doesn't have to hold the unit the entire time, as long as their ear clip is connected to them and that clip is connected to the machine, they have the freedom to set down the unit near them, hold it, put it in a pocket, or use the belt clip on the device. The ear clip connects to the unit by a cord. The participant will be asked to complete the TENS Microcurrent Unit Daily Recording Diary to document when the device was used and where on their ear, as well as the times of starting/ending sessions. Participants will be emailed daily via REDcap survey distribution for completion. The study coordinator will contact the patient 2 times over the 4 weeks to check in for adverse events that would be promptly recorded and reported and to remind them to keep using the device, but a coordinator contact will be on the instructions printout should they need to report any AEs/device issues prior to the check-in. Problems may also be reported on the daily recording diary, upon which study team members will receive a notification. The next visit will be scheduled, and payment will be processed.

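### The PI's arrhythmia review of the HRV recordings has no deadline and sits in the data-analysis portion of the study, so any referral is delayed by an unstated time

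*Protocol*

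**What the plan says.** All of the following is in the protocol.

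- **Timing of the review** (Pertinent Results and Incidental Findings, Q5, Arrhythmia findings, item 1): "HRV measurements done by a coordinator will be reviewed by the PI for evidence of arrhythmia during the data analysis portion of the study".
- **Seriousness** (same item): "Arrhythmia findings may reveal a significant risk of a serious health condition". The sentence goes on to say that further work-up is needed before anything is conclusive, and the bullet before it says that one test cannot settle what an arrhythmia means.
- **Trigger for referral** (Q3 of the same section): "Upon review of the HRV measurements, the PI will contact participants/parents and engage in proper referral procedures if there is evidence of arrhythmia".
- **Timing of communication**: the form asks "To whom and by whom the findings will be communicated, when, and how". Item 4 of the arrhythmia answer says that the PI reports abnormal measurements "to the participant and/or their parents upon review of the measurements".
- **What families are told at consent** (item 2): "the investigator will contact them/their parents upon the instance of abnormal findings".
- **Expected effect on participation** (item 4): a participant with such a finding is to be withdrawn, but "analysis of these measurements will not happen immediately upon collection, so this is an unlikely occurrence". Risks, Discomforts, Potential Harms and Monitoring, Q5 also allows the PI to withdraw someone whose HRV recording is abnormal.
- **Availability of the file** (Study Procedures, Q7, Week 0 Visit): "Upon completion of the study visit, HRV data from the device will be exported into software-compatible files on a VCU managed computer".

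**The concern.** The answer to the form's question about timing is circular. Communication follows the review, and the review is tied to a phase of the study that has no date. A 12-21 year old whose baseline recording shows an arrhythmia could complete the 4 weeks of home use before anyone looks at the rhythm, with no stated limit after that. This matters most for a participant without symptoms, because one with symptoms has other routes to attention.

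Two further consequences follow. The withdrawal provisions depend on a read that will usually come after participation has ended. And the protocol describes the risk of not knowing about an arrhythmia only as a failure to measure HRV properly. On that reasoning an early read would also help the study, because an unusable baseline recording would be noticed before four weeks of participation are spent on it.

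**Working it through.** The protocol states no figure for the delay, so there is none to reproduce. The check is a reading of the provisions against one another, followed by arithmetic on the cost of the fix.

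**1. Does anything date the review?** No. Item 1 names a phase and gives no date. Q3 and item 4 start contact from the review. Referral therefore cannot come before a review whose time is not fixed.

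**2. Does another provision require an earlier read of the rhythm?** None in the protocol text does.

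| Provision | What it does | Does it read the individual rhythm? |
|---|---|---|
| Study Procedures, Q7: two coordinator check-ins and diary alerts | Picks up problems that participants report | No |
| Risks, Discomforts, Potential Harms and Monitoring, Q4: general health monitoring | Ordinary clinical oversight; does not mention the recordings | No |
| Data and Safety Monitoring, Q9-Q10: DSMB | May see vagal modulation data every 6 months, if data and members' time allow; looks for trends | No |
| Data Confidentiality and Storage, Q9: linkage key kept until closure | Keeps contact possible | No, and sets no time |

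**3. Does the workflow force the wait?** No. The file is exported when the visit ends, so it can be read at once.

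**4. Would a short deadline fall inside participation?** 5 working days is at most 7 calendar days, barring holidays. The visits are 4 weeks apart: 4 × 7 = 28 days. Since 7 < 28, a baseline finding could be acted on while the participant is still in the study.

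**5. What would the reads cost?**

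- Number of recordings, from Study Population, Q1 and Q3. The floor is 28 completers: 28 × 2 visits = 56. The ceiling is the cap of 100 people: 100 × 2 = 200. The ceiling will not be reached, because the 100 includes screen failures and dropouts.
- Length of one recording, from Study Procedures, Q7: 15 + 5 + 30 + 15 + 5 = 70 minutes.
- Reading time: 5-15 minutes per recording. This is an assumption; the protocol gives no figure.

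| Recordings | At 5 min | At 15 min |
|---|---|---|
| 56 | 280 min = 4.7 h | 840 min = 14 h |
| 200 | 1,000 min = 16.7 h | 3,000 min = 50 h |

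**6. What cannot be computed.** The protocol gives no arrhythmia rate and no date for the data-analysis portion. The number of participants affected and the length of the delay are therefore both unknown.

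**The case against.** The strongest reply is that the protocol is open about this. It states who reviews, what triggers contact, how the family is reached and that a referral follows, and it says that the read will not be immediate. Without the trial these recordings would not exist, so the delay is measured against a faster research read and not against usual care. Pacemakers, defibrillators and unstable medical conditions are excluded. An early screen could also produce non-specific referrals and distress, especially where the device exports only interbeat intervals.

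Most of this stands as a limit on the size of the point. It does not remove the point, because disclosing a delay does not shorten it.

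Several stronger readings are tempting, and the protocol does not support them:

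- **That all reads are held until the last participant finishes.** A reader might infer this from the reference to the data-analysis portion. Nothing says that recordings are batched, and the DSMB's possible 6-monthly look at vagal modulation data suggests that some processing may happen during the study. The only stated limit is that analysis is not immediate.
- **That the protocol contradicts itself.** It provides for withdrawal on an abnormal finding and then says that this will seldom arise. The two statements are consistent.
- **That home stimulation before the read is itself a hazard.** The device is designated non-significant risk, and nothing in the protocol links it to arrhythmia.
- **That arrhythmia on the recording is a confirmed serious condition.** The protocol says that further testing is needed.
- **That no study document sets a time.** The HRV measurement form and the consent and assent forms are listed but not shown. The point holds for the protocol text.

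**Conclusion.** The point holds as a weakness in a disclosed timing choice. As written, the PI's arrhythmia review has no deadline, contact and referral depend on it, and the protocol expects findings to surface rarely during participation. The consequence is a referral delayed by an unstated time, mainly for a participant without symptoms, and withdrawal provisions that will seldom operate. The wording of the plan supports this with high confidence. The size of the harm is unknown and is not claimed.

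This is a participant-safety and procedural matter. It does not affect the endpoint or the sample size. It deserves correction because the correction is cheap and moves forward a review that is already promised.

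**What to change.** In Pertinent Results and Incidental Findings, Q3 and Q5:

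- State that the PI screens each exported recording for arrhythmia within a fixed short time of each visit, for example 5 working days after Week 0 and after Week 4, using the ECG where the device provides it and interbeat intervals otherwise.
- Log the date of each read in REDCap.
- Give the same time frame in the consent discussion (item 2).
- Amend the last sentence of item 4, which would no longer be true.

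Dispensing the device on the baseline day and the later Kubios analysis stay as they are.

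The cost is amendment wording and PI reads spread through recruitment, with some files opened twice. The hours in the table above are totals, and part of them replaces the review already planned. If none of it did, the most the change would add is 50 hours under the assumed reading time, and a 70-minute recording may take longer than assumed. Where only interbeat intervals are exported, the early screen is coarser than an ECG read and may prompt some non-specific referrals.
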